Treatment fidelity⁴³ for both study groups will be assured first, though the use of a scripted manual for each group session will be used during RA training sessions which will include role-playing with simulated participants until competency in delivery of group sessions is demonstrated. A log of the time taken for each group session will be kept to ensure equivalent treatment dose across all sessions. Debriefing will be conducted following each session to identify any areas for improvement. A protocol checklist will be used to ensure that content is completely and consistently covered and all outcome measures are collected at baseline, 1,2, 3, 6, and 12 months.

F. Data Analysis

The overall analytic design is a mixed design model where participants are randomly assigned to one of two intervention or comparison arms. The response over time of the participants will likely be correlated, therefore covariance patterns over time to be considered include compound symmetry, autoregressive, exponential (allows for unequally spaced times) and unstructured. The unstructured covariance pattern allows for less variation in the outcome variable (e.g., days engaged in activities) at baseline—a condition which may occur and will be evaluated.

Aim 1: Perception of activity trackers will be determined by participants' responses to open-end surveys. The responses from these surveys will be analyzed using content analysis to explore narrative responses for each open-ended question for commonalities and placed in emerging patterns or themes.

Aim 2: The test of effectiveness for each intervention arm is assessed by evaluating the treatment group by time interaction with two a priori contrasts (one for each arm) comparing the one-year follow-up mean to the baseline mean (essentially a paired t-test in the context of ANOVA). If an intervention is effective, we expect an initial rapid and sustained increase in the

Study Title: Increasing Activity Post-Kidney Transplant with SystemCHANGE™

IRB Protocol Number: 2017B0084

Approval Date: 10-22-18

NCT03191630

Version: 08/28/2018

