numbers of steps/day; a subsequent return to near baseline levels would indicate that the intervention is not effective. To quantify the effectiveness of each arm and compare the effectiveness of the two arms at one-year follow-up, we will compute 95% confidence intervals of the changes in the primary outcome variable. The same approach will be used to quantify the effectiveness of the intervention and control groups on the secondary outcome variables. For Aim 2, the primary outcome will be the number of steps per day; secondary outcomes include distance traveled in 6 minutes, health outcomes (blood pressure, heart rate, body mass index, waist circumference) and quality of life (SF-12). Baseline characteristics of participants will be ascertained prior to randomization and all outcomes measured at baseline, 3 months (Follow-up 1), 6 months (Follow-up 2) and 12 months (Follow-up 3). A total of 60 participants will be randomized to either the SystemCHANGE™ + activity tracker intervention or activity tracker control group. Thus, the study has a classical repeated-measures design. Power calculations are based on two-sided t-tests with type-I error rates of 0.05. Effect sizes within arm will be small with standardized differences ranging from 0.37 to 0.58; we assumed a correlation between repeated measures of 0.7. While we used changes from baseline to 12 months to calculate power, we will analyze data for this aim by evaluating the average number of steps/day at baseline and at each follow-up. Results will be analyzed based on intention-to-treat. Using means and standard deviations for accelerometer-based numbers of steps per day from Dontje and colleagues,⁷ we estimate the activity tracker control group to record 6326 ± 2906 steps/day at baseline and 7562 ± 3785 steps/day at 12-months follow-up. In the context of repeated measures ANOVA, using a t-test within arm to detect change from baseline to 12-months, power is 0.575. Because no data exist for determining the effect on steps/day of the SystemCHANGE™ + activity tracker intervention, we assumed that the differences between the means of the two arms at 12 months might conservatively be between 346 and 662 steps/day. Thus, we expect the intervention group to record 6326 ± 2906 steps/day at baseline and between 7908 ± 3785 and 8224 ± 3785 steps/day at 12-months follow-up. Using a within arm t-test, power is 0.798 to 0.918. Change from baseline in each arm will quantify the effectiveness of each in improving the primary outcome. Although this study is not powered to detect differences between the arms at 12 months, we will be able to compare the relative effectiveness of each arm at one-year follow-up and will compute 95% confidence intervals of the changes in outcome variables. We expect that each of these confidence intervals will include the mean of the comparison intervention. If differences between interventions are detected, we expect that the difference will be attributable to (1) fewer numbers of steps/day at baseline compared to the Dontje study⁷ and/or (2) a larger effect on the number of steps/day of the SystemCHANGE™ + activity tracker intervention at 12 months. Data loss due to participant failure to complete all measures is a serious concern in every clinical investigation. Any missing data will be identified at the time of collection and rectified by asking participants to provide the necessary information. However, because subjects have the right to refuse to answer questions (informed consent), we will code null values differently from 'refuse to answer' and 'not applicable'. We will also explore demographics of participants for the effects of influencing outcomes. Missing step-data will occur when participants forget to wear or charge devices overnight; we will identify these missing data prior to the group visit so participants can give information on the reasons for missingness.

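### Objective (b) asks for a comparison with tracker-only, but Aim 2 tests each arm against its own baseline and defines no between-arm estimate or interval

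*Combined protocol and SAP*

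**What the plan says.** Section I, objective (b), is comparative: improvement from baseline to 3, 6 and 12 months in the SystemCHANGE plus tracker arm, set against a tracker-only control.

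Section III.F, Aim 2, assesses the effectiveness of each arm through the group-by-time interaction, evaluated with "two a priori contrasts (one for each arm) comparing the one-year follow-up mean to the baseline mean (essentially a paired t-test". It adds that a return to near-baseline step counts would mean the intervention is not effective, so the yardstick is the arm's own baseline. Later it repeats: "Change from baseline in each arm will quantify the effectiveness of each in improving the primary outcome".

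The plan also intends to compare the arms. To quantify each arm's effect and "compare the effectiveness of the two arms at one-year follow-up, we will compute 95% confidence intervals of the changes in the primary outcome variable". It does not say that an interval will be computed for the difference between the two changes. The way it expects the intervals to behave shows that they are per-arm intervals: "We expect that each of these confidence intervals will include the mean of the comparison intervention". The same approach is to be used for the secondary outcomes.

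All the power figures are within-arm, and the plan states that "this study is not powered to detect differences between the arms at 12 months".

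**The concern.** A within-arm contrast asks whether steps changed from baseline. Objective (b) asks whether they changed more with SystemCHANGE than with the tracker alone. These questions differ most when the control arm is itself expected to improve, as it is here: "we estimate the activity tracker control group to record 6326 ± 2906 steps/day at baseline and 7562 ± 3785 steps/day at 12-months follow-up". A significant rise in the intervention arm would then be the likely result whether or not SystemCHANGE does anything.

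The randomised comparison is what protects against crediting SystemCHANGE with the effect of the tracker, of study contact or of time. As written, it has no pre-specified estimate or interval for the primary outcome or any secondary outcome. Readers would be left to compare two separate tests, or to set one arm's interval against the other arm's mean. Neither is a valid test of a difference.

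**Working it through.** **Inputs (section III.F, Aim 2).** SD 2,906 at baseline and 3,785 at month 12, used for both arms; correlation 0.7; two-sided alpha 0.05; control mean 6,326 rising to 7,562; intervention mean 6,326 rising to 7,908–8,224; assumed month-12 difference 346–662; 60 randomised. The power text gives no number per arm. I use 30 (no loss) and 25, both as assumptions.

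**1. The plan's own power.** SD of change = √(2,906² + 3,785² − 2 × 0.7 × 2,906 × 3,785) = √7,372,167 = 2,715. Two-sided paired-t power (noncentral t):

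| True change (steps/day) | Plan | n = 25 | n = 30 |
|---|---|---|---|
| 1,236 | 0.575 | 0.589 | 0.674 |
| 1,582 | 0.798 | 0.798 | 0.870 |
| 1,898 | 0.918 | 0.918 | 0.959 |

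The two intervention figures reproduce at 25 per arm and the control figure comes close. This confirms that the power statements are paired, within-arm calculations.

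**2. How much of the expected rise belongs to the control condition.** Control: 7,562 − 6,326 = 1,236. Intervention: 7,908 − 6,326 = 1,582, to 8,224 − 6,326 = 1,898. Shares: 1,236/1,582 = 78% and 1,236/1,898 = 65%.

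**3. What the contrasts show if SystemCHANGE adds nothing.** Both arms then rise by 1,236. The intervention contrast is significant with the probability in the first row of the table: 0.575, 0.589 or 0.674. In simulation (400,000 replicates) with 30 per arm:
- intervention significant and control not: 22%;
- exactly one arm significant: 44%;
- intervention arm's 95% interval excludes the control mean change: 16%;
- at least one arm's interval excludes the other arm's mean: 19%;
- direct between-arm test significant: 5%, as it should be.

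At 25 per arm these are 24%, 48%, 16%, 19% and 5%. A single-arm interval ignores the sampling error of the other arm's mean, which is why it excludes that mean too often.

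**4. What the missing estimate would deliver.** SE of the difference in change = 2,715 × √(2/n).
- n = 30: SE 701; 95% half-width 1,403; power 0.077 for 346 and 0.153 for 662.
- n = 25: SE 768; half-width 1,544; power 0.073 and 0.135.

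With baseline as a covariate, the residual SD is 3,785 × √(1 − 0.7²) = 2,703, and the half-widths are about 1,400 and 1,540, practically the same. The enrolment table in section III.B adds up to 32 intervention and 28 control participants; that split leaves power at 0.077 and 0.153.

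**The case against.** The strongest reply is that a between-arm comparison is intended. The group-by-time interaction is named, and in a two-arm model that interaction is the comparison of change. The text says more than once that the arms will be compared. It never says that a significant intervention-arm contrast shows benefit over control. Section III.C says step counts will be adjusted for baseline, which makes most sense for a between-arm comparison. The study is a pilot that discloses its low between-arm power. With both arms' changes and intervals reported, a reader could work out the difference and its interval.

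Part of this stands. The intent to compare is real. The 0.575 is correct power against zero change and misleads only if read as benefit over control. The half-widths in the working are also best cases: they assume independent participants, whereas sessions run in groups of 10–12. With groups of 10 and an assumed intraclass correlation of 0.01, 0.05 or 0.10, the factor √(1 + 9 × ICC) turns 1,403 into about 1,465, 1,690 or 1,934.

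It does not remove the point. The sentence that names the interaction also says how it is evaluated, and both contrasts are within-arm. The difference between them, which is the interaction contrast, is not listed. The expected behaviour of the intervals confirms that they are per-arm. Low power limits what can be concluded; it is no reason to leave the randomised estimate undefined. An analysis that readers must reconstruct is not pre-specified.

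**Conclusion.** The concern holds. The stated rule for effectiveness in Aim 2 does not answer objective (b). This goes beyond missing detail, because the tests and intervals that are written down address a different question. On the plan's own assumptions, the intervention contrast would be significant with probability of about 0.58 to 0.67 when SystemCHANGE adds nothing. Reading one arm's interval against the other arm's mean would signal a false difference about 16–19% of the time instead of 5%.

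These sizes rest on the plan's SDs and correlation holding equally in both arms, on 25 or 30 analysed per arm, and on independent participants. The conclusion that the contrasts do not address the objective depends on none of these. Because it affects the primary analysis of the effectiveness objective and carries over to every secondary outcome, it must be corrected before analysis.

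**What to change.** In section III.F, Aim 2, define the primary estimate as the single between-arm contrast in steps/day at month 12, with one 95% confidence interval, from the planned mixed model. Choose one form:

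- **Preferred:** model months 3, 6 and 12 with baseline steps as a covariate and report the month-12 arm difference. This fits the baseline adjustment announced in section III.C.
- **Alternative:** keep baseline as a response and report the difference between arms in change from baseline to month 12, which is the group-by-time contrast.

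Do not use baseline as both a response and a covariate. Use the same contrast for each secondary outcome. Report the month-3 and month-6 arm differences from the same model, since objective (b) names those times. Label within-arm changes as descriptive.

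Replace the sentence expecting each arm's interval to contain the other arm's mean with the between-arm interval and its expected half-width: about 1,400 steps/day at 30 analysed per arm, about 1,540 at 25. Mark both as illustrative and as assuming no clustering by session group.

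The cost is wording only, with the same data, visits, sample size and model. The drawback is a visibly wide interval and power of about 7–15% for the range in the plan ("we assumed that the differences between the means of the two arms at 12 months might conservatively be between 346 and 662 steps/day"), consistent with what the plan already concedes.
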